#### **9.9.1.1. All TEAEs**

Subject incidence of TEAEs will be summarized in 2 separate tables by:

- SOC and PT
- PT only

If a subject reports a TEAE more than once within a SOC or PT, the TEAE will be reported only once for that SOC or PT.

For summaries by SOC and PT, SOC's will be sorted in alphabetical order and PT's within each SOC in

descending order of overall frequency. For summaries by PT only, PTs will be sorted in descending order of overall frequency.

Subject incidence of TEAEs presented by SOC and PT will be broken down further by maximum severity (refer to section 9.9.1.2) and worst relationship to study drug (refer to section 9.9.1.3). Handling of missing or partially missing start and stop dates for TEAEs are described in **Error! Reference source not found..**

#### **9.9.1.2. SEVERITY**

Severity, as determined by the Investigator, will be classed as mild, moderate, severe, life-threatening or fatal. If a subject reports a TEAE more than once within SOC or PT, the AE with the worst severity will be used in the corresponding severity summaries.

AE with missing severity will be reported as missing into the summaries.

#### **9.9.1.3. RELATIONSHIP TO STUDY DRUG**

Relationship to study drug, as indicated by the Investigator, will be classed as “not related” or “related” (i.e., related or suspected to be related”). If a subject reports the same AE more than once within SOC or PT, the AE with the worst case relationship to study drug will be used in the corresponding relationship summaries.

AE with a missing relationship to study drug will be reported as related into the summaries.

#### **9.9.1.4. ADVERSE EVENTS WITH AN OUTCOME OF DEATH**

A listing including all AEs with an outcome of death will be provided.

#### **9.9.1.5. SERIOUS ADVERSE EVENTS**

A listing including all SAEs will be provided.

#### **9.9.1.6. TEAEs LEADING TO DISCONTINUATION OF STUDY DRUG**

Subject incidence of TEAEs leading to permanent discontinuation of study drug will be summarized by SOC and PT. Usually, for each subject who discontinued early from study drug due to an AE, only one AE has an action taken of ‘drug withdrawn’ corresponding to the subject’s primary reason of discontinuation from study drug. In the event that more than one AE has an action taken of ‘drug withdrawn’ for a subject, subject will count only once within a SOC or PT.

A listing including all TEAEs leading to permanent discontinuation of study drug will be provided.

#### **9.9.1.7. TEAEs OF SPECIAL INTEREST**

TEAEs of special interest will be summarized and may include the terms or categories noted below. The list of categories of special interest will be finalized prior to the database extraction (soft DBL)

- Anxiety

- Confusion
- Convulsions
- Depressed Consciousness
- Depression and Suicidality
- Psychotic and dissociative disorders
- Substance-related disorders
- Impaired attention or cognition
- Parasomnias
- Respiratory Failure and Respiratory Depression

A listing presenting subjects with TEAEs of special interest will be provided..

## 9.9.2. LABORATORY EVALUATIONS

Results from the central laboratory will be included in the reporting of this study for:

- **Hematology, Serum chemistry (excluding electrolytes):** Main Study baseline, end of DB RWP, OLE baseline, and end of OLE Period
- **Electrolytes (i.e., sodium, potassium, magnesium, and calcium):** Main Study baseline, each Main Study in-clinic scheduled visit, OLE baseline, OLE Week 12, and end of OLE Period
- **Urinalysis:** Main Study baseline, end of DB RWP, OLE baseline, and end of OLE Period
- **Pregnancy test:** serum at Main Study screening visit, urine at each Main Study in-clinic scheduled visit, serum at OLE screening visit, and urine at each OLE in-clinic scheduled visit
- **Drug screen:** Main Study screening visit, each Main Study in-clinic scheduled visit, OLE screening visit, and each OLE in-clinic scheduled visit
- **Alcohol screen:** Main Study screening visit, each Main Study in-clinic scheduled visit, OLE screening visit, and each OLE in-clinic scheduled visit

An authorized back-up laboratory may be used if necessary as an emergency laboratory. A list of laboratory assessments to be included in the outputs is included in APPENDIX 5.

See section 6.3 for handling of retests and unscheduled measurements.

Laboratory results will be reported in SI Units.

For **hematology, serum chemistry, electrolytes** and **urinalysis data** the following summaries will be provided across all study periods by visit:

- Observed and change from baseline (Main Study baseline and OLE baseline) for quantitative measurements
- Observed for qualitative measurements

- Shift table from baseline (Main Study baseline and OLE baseline) according to normal reference range criteria (for quantitative measurements)

The same summaries will be repeated on the RWP SAF by treatment group.

For hematology, serum chemistry, electrolytes and urinalysis data, the summaries of change from baseline during the OLE will differ depending on subjects:

- For rollover subjects: change from baseline = OLE measurements – Main Baseline
- For re-entry subjects: change from baseline = OLE measurements – OLE Baseline

For electrolytes, a box plot of change from baseline will also be provided by pre-randomization group across all study periods based on the SAF.

A listing of subjects with abnormal value(s) according to normal range criteria and a listing of subjects with alanine aminotransferase (ALT) or aspartate aminotransferase (AST)  $\geq 3xULN$  and total bilirubin  $> 2xULN$ , as well as subjects with Creatinine  $\geq 176$  and subjects positive for alcohol screen, urine drug screen and pregnancy assessments at screening will be also provided based on the SAF.

All laboratory results, including pregnancy test, drug screen, and alcohol screen, will be presented in subject data listings.

#### **9.9.2.1. LABORATORY SPECIFIC DERIVATION**

- Multiple of upper limit of normal (ULN) = result / ULN

#### **9.9.2.2. LABORATORY NORMAL REFERENCE RANGES**

Quantitative laboratory measurements will be compared with the relevant laboratory reference ranges in SI units and categorized as:

- Low: result  $<$  lower limit of normal (LLN)
- Normal: result within the laboratory normal reference range (upper and lower limit included)
- High: result  $>$  ULN

#### **9.9.3. ECG EVALUATIONS**

A standard 12-Lead ECG will be recorded with the subject resting in supine for at least 5 minutes. ECGs will be performed during the Main Study screening visit, end of the DB RWP visit (or at early termination), OLE screening visit, and end of OLE visit. Results from the central ECG Reading Centre will be included in the reporting of this study. The following ECG parameters will be reported:

- PR Interval (msec)
- RR Interval (msec)
- QRS Interval (msec)
- QT Interval (msec)

- QT Bazett's correction (QTcB) Interval (msec) [derived]
- QT Fridericia's correction (QTcF) Interval (msec) [derived]
- HR (beats per minutes [bpm])
- Axis (degree)
- Overall assessment of ECG:
  - o Normal
  - o Abnormal, Not Clinically Significant
  - o Abnormal, Clinically Significant

The following summaries will be provided for ECG data across all study periods::

- Observed and change from baseline (Main Study baseline and OLE baseline) by visit (for quantitative measurements)
- Incidence of markedly abnormal criteria by visit

All ECG parameters results will be listed over time.

A listing of subjects meeting markedly abnormal criteria as well as a listing of subjects with abnormal ECG overall assessment will also be provided based on the SAF.

#### 9.9.3.1. ECG SPECIFIC DERIVATIONS

- $\bar{A}\bar{A}\bar{A}\bar{A} \text{ (msec)} = \frac{\bar{A}\bar{A} \text{ (}\bar{A}\bar{A}\text{)}}{\sqrt[3]{\bar{A}\bar{A} \text{ (}\bar{A}\bar{A}\text{)}/1000}}$
- $\bar{A}\bar{A}\bar{A}\bar{A} \text{ (msec)} = \frac{\bar{A}\bar{A} \text{ (}\bar{A}\bar{A}\text{)}}{\sqrt{\bar{A}\bar{A} \text{ (}\bar{A}\bar{A}\text{)}/1000}}$

#### 9.9.3.2. ECG MARKEDLY ABNORMAL CRITERIA

Markedly abnormal quantitative ECG measurements will be identified in accordance with the following predefined markedly abnormal criteria ([Guidance for industry: E14: clinical evaluation of QT/ QTc interval prolongation and proarrhythmic potential for non-antiarrhythmic drugs.](#)):

- Observed values for QT interval, QTcB interval and QTcF will be classified as for both the Main Study baseline and OLE baseline:
  - o > 450 msec with no pre-existing condition i.e. baseline ≤ 450 msec
  - o > 480 msec with no pre-existing condition i.e. baseline ≤ 450 msec
  - o > 500 msec with no pre-existing condition i.e. baseline ≤ 450 msec
- Change from baseline for QT interval, QTcB interval and QTcF will be classified as for both the Main Study baseline and OLE baseline:
  - o >30 msec increase from baseline

- >60 msec increase from baseline

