9.11.2 Other Safety Analyses

Vital Signs

For each vital sign parameter, summary statistics will be provided for observed and change from baseline values by scheduled visit.

Confidential Page 88 of 148

Clinical Trial Protocol: 15-006 Amendment 5

Physical Examinations

Observed and change from baseline values for weight will be summarized descriptively by scheduled visit.

12-lead ECG

Observed and change from baseline values for ECG intervals will be summarized descriptively. QT abnormalities will be assessed; the number and percent of subjects with values or change from baseline values exceeding certain thresholds will be tabulated.

Laboratory Evaluations

Observed and change from baseline laboratory evaluations will be summarized descriptively.

C-SSRS

C-SSRS parameters will be tabulated by scheduled visit.

PHQ-9

Depression severity based on PHQ-9 will be summarized by scheduled visit.

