## 6.2. BASELINE

- **Weekly average of Cataplexy Attacks:** For this efficacy endpoint, baseline will be defined as the average number of daily cataplexy attacks from days with non-missing data within the 2 weeks OL SDP, multiplied by 7.

- **Epworth Sleepiness Scale (ESS), 36-Item Short Form Health Survey (SF-36), and European Quality of Life (EuroQoL) 5 Dimensions 5 Levels (EQ-5D-5L):** For these assessments, baseline will be defined as the last non-missing measurement taken prior to or on the date of randomization (including unscheduled assessment) i.e., DB RWP Day 1.
- **Clinician Global Impression of Severity (CGIs) for Narcolepsy Overall:** For this assessment, no baseline will be defined as this scale will be collected only once during the study i.e., at the end of the OL SDP.
- **Patient Global Impression of Change (PGIc) for Narcolepsy Overall and Clinician Global Impression of Change (CGIc) for Narcolepsy Overall:** For these assessments, no baseline will be defined as these scales already assess the change in the severity of the subject’s narcolepsy overall since the end of the OL SDP. Furthermore, these assessments will be recorded only once during the study, i.e., at the end of the DB RWP.
- **Hematology, Fasting Chemistry (incl. electrolytes), Weight, Vital signs, Urine Drug Screen, Columbia-Suicide Severity Rating Scale (C-SSRS), Physical Examination, 12-Lead Electrocardiogram (ECG) and Patient Health Questionnaire-9 (PHQ-9):** For these assessments, two types of baseline will be defined:
  1. ‘Main Study baseline’ will be defined as the last non-missing measurement collected/ assessed prior to or on the same day of the first dose of study drug during the Main Study, including unscheduled measurements and retests.
  2. ‘OLE baseline’ will be defined as the last non-missing measurement collected/ assessed prior to or on the same day of the first dose of study drug during the OLE, including unscheduled measurements and retests.

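### The >480 and >500 msec QT categories reuse the ≤450 msec baseline condition, so some new exceedances of 480 and 500 msec are not counted as such

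*SAP*

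**What the plan says.** SAP 9.9.3.2 defines three observed-value categories for QT, QTcB and QTcF: "> 450 msec with no pre-existing condition i.e. baseline ≤ 450 msec", "> 480 msec with no pre-existing condition i.e. baseline ≤ 450 msec" and "> 500 msec with no pre-existing condition i.e. baseline ≤ 450 msec". The threshold climbs but the baseline condition does not. Two change categories, ">30 msec increase from baseline" and ">60 msec increase from baseline", carry no baseline condition.

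The classification is run against two baselines: "Observed values for QT interval, QTcB interval and QTcF will be classified as for both the Main Study baseline and OLE baseline". SAP 6.2 defines the Main Study baseline as "the last non-missing measurement collected/ assessed prior to or on the same day of the first dose of study drug during the Main Study", and the OLE baseline in the same way around the first OLE dose.

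SAP 9.9.3 uses these criteria for an incidence table by visit and for a listing of the subjects who meet them. It also provides a listing of subjects with an abnormal overall ECG assessment, a listing of all ECG results, and by-visit summaries of observed values. SAP 6 includes the maximum among the summary statistics.

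Protocol 9.11.2 describes the QT counts in general terms: "the number and percent of subjects with values or change from baseline values exceeding certain thresholds will be tabulated". It names no threshold and no baseline restriction. SAP 3.6, on changes from the protocol, mentions only the imputation method. Main Study exclusion criterion 13 (Protocol 4.2.2) relies on the investigator's judgement of the screening ECG and sets no numeric QTc limit, so a subject with a baseline above 450 msec can enter.

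**The concern.** A baseline condition on an outlier count usually serves to separate values that became abnormal on study from those that were abnormal at the start. A limit of 450 does this for the >450 category. For the two higher categories it goes further. It also removes subjects who started above 450 but had not yet reached 480 or 500, and whose later crossing is new.

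At stake is the accuracy of one tabulated safety output. Any error runs in one direction: the >480 and >500 rows can be too low but never too high as counts of new crossings.

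**Working it through.** There is no sample size, power or alpha figure to reproduce here. The check applies the rules of SAP 9.9.3.2 directly. Let b be the applicable baseline and p the post-baseline value, in msec.

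- Plan: >480 counts if p > 480 and b ≤ 450; >500 counts if p > 500 and b ≤ 450; change counts if p − b > 30 or p − b > 60.
- Matched rule: >480 counts if p > 480 and b ≤ 480; >500 counts if p > 500 and b ≤ 500.

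| Baseline → value | Rise | Counted by the plan as | Added by the matched rule |
|---|---|---|---|
| 440 → 505 | 65 | >450, >480, >500, >30, >60 | nothing |
| 455 → 485 | 30 | no category | >480 |
| 455 → 510 | 55 | >30 only | >480, >500 |
| 475 → 503 | 28 | no category | >480, >500 |
| 485 → 505 | 20 | no category | >500 |
| 499 → 501 | 2 | no category | >500 |

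**Extent of the gap.** Over all integer pairs with baseline 451-500 and value 451-600, the plan's >480 and >500 categories flag none. A value of 501 escapes every QT category when 501 − b ≤ 30, that is, for each integer baseline from 471 to 500. A value of 481 escapes every category when 481 − b ≤ 30, that is, for each integer baseline from 451 to 480.

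**What the upper categories add as written.** If b ≤ 450 and p > 480, then p − b > 480 − 450 = 30. If b ≤ 450 and p > 500, then p − b > 50. So everyone counted in the >480 or >500 category is already counted in the >30 msec change category against the same baseline. The two upper categories cannot flag a subject whom the change criteria miss.

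**Role of the second baseline.** A subject at 455 at screening and 445 at the OLE baseline is eligible for all three categories in the OLE. The OLE baseline gives no help at Visit 16, because that ECG falls on or before the first OLE dose and so cannot be post-baseline to it.

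**Number of subjects.** The documents give no QT or QTc distribution, so the number cannot be computed. As an assumption only, take QTc as normal with mean/SD of 415/20, 420/22 or 425/25 msec, one ECG in each of the 185 planned subjects, and no drug effect. The expected number above a threshold is 185 × P(Z > (threshold − mean)/SD).

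- Above 500: z = 4.25, 3.64, 3.00, giving 0.002, 0.03 and 0.25 subjects.
- Above 480: z = 3.25, 2.73, 2.20, giving 0.1, 0.6 and 2.6 subjects.

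The missed crossings are a subset of these. A drug effect or further ECGs would raise the figures. Protocol 6.6 schedules one post-baseline ECG in the Main Study (end of the double-blind period or early termination), and for the OLE one at Visit 18 (re-entry subjects only) and one at Visit 33 or early termination.

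**The case against.** The strongest reply is that this is a stated definition, not a slip. The SAP spells out what it means by no pre-existing condition, and all three categories then describe how far subjects who began at or below 450 msec went. Read that way the text is coherent. It does not contradict Protocol 9.11.2, which leaves the thresholds open. That much stands: the SAP never says that each row means a new crossing of that row's threshold. The reply does not meet the practical result, which is that no row counts a move from 475 to 503.

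Second, nothing is lost from the data. The values appear in the full listing and may show as the visit maximum. Rises above 30 msec put the subject in the markedly abnormal listing, and Protocol 6.6 provides a central cardiologist over-read. This also stands, and it limits the harm. A listing or a maximum is still not a count of subjects.

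Three stronger readings are tempting, and the documents do not support them.

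- A reader might infer that anyone above 450 at baseline is shut out of the observed-value categories for the whole study. The separate classification against the OLE baseline means that this need not be so.
- A reader might estimate how many subjects start above 450 and treat that as the size of the undercount. That is the wrong quantity: a missed case must also newly cross 480 or 500, and the baseline distribution is not given.
- A reader might infer that the rule hides the subjects at greatest risk, or distorts a pivotal safety result. The documents do not rank risk by baseline QT. QT is not in the provisional list of events of special interest (SAP 9.9.1.7) or among the mandatory discontinuation criteria (Protocol 6.14.1), and all safety analysis is descriptive.

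**Conclusion.** The point holds as a minor one. With one baseline limit on all three categories, the incidence table and the markedly abnormal listing can under-count new QT, QTcB and QTcF values above 480 and 500 msec. Where the rise exceeds 30 msec, the subject is still counted and listed, but only as a change. Where it is 30 msec or less, that value meets no markedly abnormal QT criterion against that baseline.

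The logic rests on the SAP text alone. The size does not: whether any subject is affected depends on a baseline distribution that the documents do not report. The expectation that few are affected rests on the assumed distributions above and on the small number of scheduled ECGs. Exclusion criterion 13 may thin the group further, by an unknown amount. Efficacy, type I error and sample size are untouched.

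**What to change.** In SAP 9.9.3.2, set each baseline condition equal to its threshold: >450 with baseline ≤450, >480 with baseline ≤480, >500 with baseline ≤500. As an alternative or in addition, tabulate all post-baseline values above 480 and 500 msec regardless of baseline, labelled as such. If progression from a baseline of 450 or less is also of interest, the present rows can be kept under a label that says so. State the denominator for each row, since the eligible group will then differ between rows.

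The cost is two numbers in the SAP with the matching programming and table labels. No new data are needed. Every subject with a baseline ≤450 also satisfies ≤480 and ≤500, so the counts can only stay the same or rise.

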#### 9.9.4. VITAL SIGNS

The following vital signs measurements will be reported for this study.

- Sitting systolic blood pressure (SBP) (mmHg)
- Sitting diastolic blood pressure (DBP) (mmHg)
- Sitting pulse rate (bpm)
- Respiratory rate (breaths/min)
- Body Temperature (°C)
- Weight (kg)
- BMI (kg/m^2) [derived]

These vital signs (with the exception of the BMI which will be calculated programmatically) will be measured during the Main Study screening visit, each Main Study in-clinic scheduled visit, OLE screening visit, and each OLE in-clinic scheduled visit. Height (cm) will be obtained at Main Study screening visit only.

The following summaries will be provided for vital signs data across all study periods

- Observed and change from baseline (Main Study baseline and OLE baseline) by visit
- Incidence of markedly abnormal criteria by visit

A listing of subjects meeting markedly abnormal criteria will also be provided based on the SAF.

##### 9.9.4.1. VITAL SIGNS MARKEDLY ABNORMAL CRITERIA

Markedly abnormal quantitative Vital Signs measurements will be identified in accordance with the following predefined markedly abnormal criteria as specified in Table 7 for both the Main Study baseline and OLE baseline.

**Table 4 Vital Signs Predefined Markedly Abnormal Criteria**

Variable (unit)	Low	High
SBP (mmHg)	≤ 90 mmHg AND change from baseline ≤ -20 mmHg	≥ 180 mmHg AND change from baseline ≥ 20 mmHg
DBP (mmHg)	≤ 50 mmHg AND change from ≤ -15 mmHg	≥ 105 mmHg AND change from baseline ≥ 15 mmHg
Heart rate (bpm)	≤ 50 bpm AND change from baseline ≤ -15 bpm	≥ 120 bpm AND change from baseline ≥ 15 bpm
Weight (kg)	percentage change from baseline ≤ -7.0%	percentage change from baseline ≥ 7.0 %

Note: bpm: Beats per minute. DBP: Diastolic Blood Pressure. kg: kilogram. mmHg: Millimeter of mercury. SBP: Systolic Blood

Pressure.

## 9.9.5. OTHER SAFETY ASSESSMENTS

### 9.9.5.1. COLUMBIA-SUICIDE SEVERITY RATING SCALE

The C-SSRS is a widely used measure of suicidal ideation and behavior. The instrument reliably predicts a potential suicide attempt in those who had previously attempted suicide and is able to determine clinically meaningful points at which a person may be at risk for an impending suicide attempt (Posner *et al* 2011, Nilson *et al* 2012).

The Screening/Baseline version of the C-SSRS will be administered to subjects at the Main Study screening visit.

The Since Last Visit version of the C-SSRS will be administered to subjects at every scheduled in-clinic visit after the Main Study screening visit up to the OLE Safety Follow-up visit.

The following summaries will be provided for the C-SSRS data by visit across all study periods by pre-randomization group and by treatment group:

- Number and percentage of subjects with any suicidal ideation as well as broken down by type of suicidal ideation
- Number and percentage of subjects with any suicidal behavior as well as broken down by type of suicidal behavior
- Number and percentage of subjects with any suicidal behavior (i.e., having responded yes to any of the 4 types of suicidal behavior) or any suicidal ideation (i.e., having responded yes to any of the 5 types of suicide ideation); a subject having reported both suicidal behavior and suicidal ideation will be counted only once
- Number and percentage of subjects with self-injurious behavior without suicidal intent.

Missing data will not be imputed. All C-SSRS parameters will be presented in the subject data listing.

### 9.9.5.2. PATIENT HEALTH QUESTIONNAIRE-9

The PHQ-9 is a nine-item depression scale developed based on the nine diagnostic criteria for major depressive disorder in the Diagnostic and Statistical Manual Fourth Edition (DSM-IV) (Kroenke *et al* 2001, Kroenke *et al* 2010). Responses to each item range from 0 = not at all to 3 = nearly every day. The instrument can be administered in person, by telephone or can be self-administered and is used to facilitate diagnosis of major depression and assessment of symptom severity. The PHQ-9 will be assessed at Main Study screening visit, start of the OL OTTP visit (day 1), week 2, week 4, week 6, week 8, week 10, end of OL OTTP visit (week 12), end of OL SDP visit (week 14), end of DB RWP/ Early Termination visit (week 16), Main Study Safety Follow-up visit (week 18), OLE screening visit, OLE week 12, end of OLE/Early Termination visit (OLE week 24), and OLE Safety Follow-up visit (week 26).

The PHQ-9 total score is the sum of 9 item-scores and can range between 0 and 27 with higher scores indicating greater severity of depression (1-4 = minimal depression; 5-9 = mild depression; 10-14 = moderate depression; 15-19 = moderately severe depression; and 20-27 = severe depression). If 3 or

more items are left unanswered, the total score will not be computed. If 1 or 2 items are left unanswered, a prorated score will be calculated. The prorated score is calculated as the sum of the scores of the items that were answered to get a partial raw score. Then, the partial raw score will be multiplied by the total number of items on the PHQ-9 (i.e., 9) and divided by the number of items that were actually answered (i.e., 7 or 8). If the result is a fraction, it will be rounded to the nearest whole number.

PHQ-9 total score and change from baseline (Main Study baseline and OLE baseline) will be tabulated by visit across all study periods by pre-randomization group and by treatment group.

